14.2 Primary Clinical Objective and Sample Size Justification

Progression Free Survival (PFS): Progression-free survival is defined as time from randomization until time of progression or death, whichever comes first. Patients who stop protocol therapy (either fulvestrant or ganetespib or both) for a reason other than progression or death should continue to be followed for progression per Study Calendar D. For subjects who do not progress or die, PFS will be censored at the time of last tumor evaluation before initiation of alternative anti-cancer treatment.

Analysis Population: All randomized patients will be included in the analysis of PFS. The analysis will be conducted based on intention to treat (ITT). However, data imputation will not be used for PFS. So patients with no follow-up at all will be censored for PFS at the date of randomization.

If the interim safety analysis indicates that the starting dose of ganetespib should be decreased to 175 mg/m², these patients will be combined with the patients who received a starting dose of 200 mg/m² in the ITT analysis. That is, all randomized patients will be included in the ITT analysis, regardless of starting dose and regardless of whether or not treatment was stopped early for any reason.

Power Calculation

The primary objective of this randomized, phase II study is to investigate whether ganetespib, when given in combination with fulvestrant, improves progression-free survival (PFS) compared to fulvestrant alone, in patients with ER-positive, metastatic breast cancer. This study will have a 1:2 randomization ratio: 24 patients will be randomized to Arm A (fulvestrant alone) and 47 patients will be randomized to Arm B (fulvestrant + ganetespib), for a total of 71 randomized patients. The expected accrual rate is ~3.5 to 4.5 patients per month over a period of ~20 months.

As this is an exploratory phase II study, no interim efficacy analyses are planned and there are no early stopping rules for efficacy (or lack of efficacy) in this study.

The primary comparison will be a one-sided log rank test of whether PFS is longer in patients randomized to Arm B (fulvestrant + ganetespib) than those randomized to Arm A (fulvestrant).

CONFIDENTIAL

This document is confidential. Do not disclose or use except as authorized.

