14.4 Analysis of Secondary Clinical Endpoints

Safety and toxicity: All patients who received at least one dose of protocol therapy (fulvestrant, ganetespib, or both) will be included in the safety/toxicity analysis. Toxicity will be graded according to NCI CTCAE, Version 4.0. The proportion of patients who experience each type and grade of toxicity will be presented in tabular form. Toxicity will be described separately in Arm A (pre-crossover), Arm C (post-crossover), and Arm B.

Objective Response Rate: All patients with measurable disease at baseline will be included in the analysis of response rate. Response will be assessed using RECIST 1.1, as described in Section 10. The response rate will be calculated separately in Arms A, B, and C. Response rates in Arm A and Arm B will be compared using a one-sided Fisher exact test. An intent to treat analysis will be used, so all patients randomized in the measurable disease stratum will be used in the

analysis; patients with no follow-up response evaluation will be assumed to be non-responders. Assuming that 57 patients are entered in the measurable disease stratum, there will be 81% power to decide that the ganetespib arm has a better response rate if the true response rates on the two arms are as different as 36% and 5%, or 44% and 10%.

Clinical benefit rate: Clinical benefit will be defined as CR + PR + SD \geq 6 months. All patients will be included in the analysis of clinical benefit. CBR will be calculated separately in Arms A and B, and compared using a one-sided Fisher exact test. All patients randomized on study will be used in this analysis, and patients with no follow-up response evaluation will be assumed not to have clinical benefit. With 71 patients randomized, there will be 80% power to decide that the ganetespib arm has a better clinical benefit rate if the true benefit rates on the two arms are as different as 63% and 30%, or 73% and 40%.

Overall survival: Overall survival is defined as duration of time from randomization to death due to any cause, or censored on the date last known alive. All randomized patients will be included in the analysis of OS. OS will be estimated separately in Arm A and Arm B. OS will be analyzed at the same time as the final analysis of PFS, although it is acknowledged that the percent of survival censoring at that time will be larger than the percent of PFS censoring, and this will limit the power to detect survival differences between the arms.

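### The one-sided Fisher exact test for ORR and CBR is valid but conservative; a one-sided Boschloo exact test at 0.05 would add about 4.5 to 8 points of power

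*Combined protocol and SAP*

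**What the plan says.** Section 14.4 covers both comparative response endpoints. For the objective response rate (ORR): "Response rates in Arm A and Arm B will be compared using a one-sided Fisher exact test". For the clinical benefit rate: "CBR will be calculated separately in Arms A and B, and compared using a one-sided Fisher exact test".

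The ORR power statement begins: "Assuming that 57 patients are entered in the measurable disease stratum, there will be 81% power"; the true rates it assumes are 36% v 5%, or 44% v 10%. The CBR statement begins: "With 71 patients randomized, there will be 80% power"; the rates are 63% v 30%, or 73% v 40%. Patients without a follow-up response evaluation count as failures in both analyses, so the denominators are everyone randomized in the relevant set.

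On allocation, section 14.2 says: "This study will have a 1:2 randomization ratio", with 24 patients on Arm A and 47 on Arm B. A one-sided 0.05 level is stated there for the log-rank test on PFS. Section 14.4 gives no level for ORR or CBR.

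**The concern.** Fisher's test conditions on the total number of responders. This design fixes the arm sizes but not that total. With small arms the conditional distribution is coarse, so the test usually cannot come close to its nominal level, and part of the permitted 0.05 goes unused. An exact unconditional test can use more of it while still respecting the limit for every common response rate.

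Comparing ORR and CBR between arms is a stated secondary objective (section 1.3). With 71 patients, several points of power on these two comparisons are worth having if the cost is only a change of test.

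**Working it through.** **Inputs.** ORR: 57 patients, which at 1:2 is 57/3 = 19 on Arm A and 38 on Arm B. CBR: 24 and 47 (section 14.2). True rates: the four pairs in section 14.4. Level: one-sided 0.05, to be confirmed in step 1.

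**Formulas.** With a responders of nA on Arm A and b of nB on Arm B:

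- Fisher p-value: p(a,b) = sum over k ≥ b of C(nB,k)·C(nA,a+b−k) / C(nA+nB,a+b).
- Fisher rejects when p(a,b) ≤ 0.05.
- Boschloo rejects when p(a,b) ≤ c, where c is the largest cut-off for which the rejection probability under a common rate π stays at or below 0.05 for every π.
- Power = sum of Bin(a; nA, πA)·Bin(b; nB, πB) over the rejection region. True level = the same sum with πA = πB = π. Worst case = its maximum over a fine grid of π.

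All tables were enumerated, so nothing is simulated.

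**Step 1: reproduce the plan.** Fisher at one-sided 0.05 gives 80.8% and 81.0% for ORR (stated: 81%) and 80.2% and 80.1% for CBR (stated: 80%). All four agree. At 0.025 the powers would be 69% to 73%, and at 0.10 they would be 88% to 91%. The plan therefore used 0.05.

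**Step 2: true level of Fisher.** The worst case is 0.0287 for ORR and 0.0327 for CBR.

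**Step 3: Boschloo.** The cut-off c on the Fisher p-value is 0.0777 for ORR and 0.0754 for CBR. The worst-case levels are 0.0495 and 0.0472. Both cut-offs exceed 0.05, so every table that Fisher rejects is also rejected by Boschloo.

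**Step 4: power** (gains are from unrounded values).

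| Endpoint | Rates, B v A | Fisher | Boschloo | Gain (points) |
|---|---|---|---|---|
| ORR, 19:38 | 36% v 5% | 80.8% | 88.5% | 7.8 |
| ORR, 19:38 | 44% v 10% | 81.0% | 87.8% | 6.8 |
| CBR, 24:47 | 63% v 30% | 80.2% | 84.7% | 4.5 |
| CBR, 24:47 | 73% v 40% | 80.1% | 84.9% | 4.8 |

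As an example, take 2 responders of 19 on Arm A. Fisher needs 14 of 38 on Arm B to reject, and Boschloo needs 12.

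**Step 5: what is paid.** True level at the plan's own control rates:

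| Common rate | Fisher | Boschloo |
|---|---|---|
| ORR 5% | 0.001 | 0.004 |
| ORR 10% | 0.011 | 0.025 |
| CBR 30% | 0.027 | 0.046 |
| CBR 40% | 0.030 | 0.046 |

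**Step 6: sensitivity to the split.** The 57 is an assumption, and 19:38 follows from the ratio without being stated. At 20:37 Fisher has 83.4% and 83.1%, and Boschloo 88.7% and 88.2%. At 18:39 Fisher has 83.0% and 81.1%, and Boschloo 88.1% and 86.7%. The ORR gain is then 5.1 to 5.6 points. It is smaller mainly because Fisher itself does better at these splits.

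**The case against.** The plan contains no error here. It names a valid test, its powers are right for that test, and the detectable differences already allow for the conservatism. The endpoints are secondary, in a trial that section 14.2 calls exploratory, and the PFS log-rank test is unaffected. All of this stands, and it limits the point to an optional improvement.

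Fisher also has a standard justification from randomization, and section 14.5 uses it for the correlative analyses, so a change would leave two exact methods in one plan. That is a matter of preference and tidiness, and it does not remove the gain.

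A reader might infer that Fisher's lost power buys nothing. That goes too far: its true false-positive rate is lower, about 0.03 at worst against just under 0.05, and section 14.4 describes no multiplicity control across the secondary endpoints. Boschloo's power comes from spending more of the nominal level.

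A reader might also infer that Fisher's true level is at most 0.03 for both endpoints. That holds for ORR at 19:38, but not for CBR, where it reaches 0.033.

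It is tempting, too, to deflate the rates by the 15% early loss in section 14.2, which makes both tests look weaker. That assumption concerns censoring of PFS. A patient censored for PFS may already have responded, and the rates in 14.4 can be read as already counting unassessed patients as failures. No such figures are used here.

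Timing is the most serious practical objection. The evaluable-disease cohort was full by 4/30/14 (section 3.1.6), amendments run into 2016, and the treatment plan describes no masking. Moving late to a test that rejects at Fisher p-values up to about 0.078 could look data-driven. This is met only if the change is fixed before anyone compares responses by arm.

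**Conclusion.** The point holds as a cheap improvement to two secondary comparisons, and not as a fault in the plan. At a one-sided 0.05 level, Boschloo's test gains 4.5 to 5 points of power for CBR. For ORR it gains 7 to 8 points if the measurable-disease patients split exactly 19:38, and 5 to 6 points at 20:37 or 18:39. The worst-case true level stays within 0.05 in every case examined, and no result significant by Fisher is lost.

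The conclusion rests on three assumptions: the 0.05 level, which is inferred because it alone among the levels tried reproduces the stated powers; 57 patients with measurable disease; and the response rates given in section 14.4.

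**What to change.** In section 14.4, for both ORR and CBR:

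- Name the one-sided Boschloo exact unconditional test in place of the one-sided Fisher exact test.
- State the one-sided 0.05 level, which is missing now. This is worth adding even if Fisher is kept.
- Restate the power (88.5% and 87.8% for ORR at 19:38; 84.7% and 84.9% for CBR), or restate the differences detectable with 80% power.
- Make and date the change before response data are compared by arm. If such a comparison has already been made, keep Fisher as the named test.

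The cost is two test statements, one level and four power scenarios. Sample size, data collection and patient care are unaffected, and standard software has the test. The downsides are the rise in the true false-positive rate from about 0.03 to just under 0.05, and a test that fewer readers will know.

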1.3 Secondary Clinical Objectives

- To assess the safety and tolerability of ganetespib in combination with fulvestrant
- To describe and compare the objective response rate by RECIST 1.1 between arms, limited to patients with measurable disease at baseline.
- To describe and compare the clinical benefit rate, defined as complete response (CR) + partial response (PR) + stable disease \geq 6 months between arms
- To describe and compare overall survival (OS) between arms

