2.3 Study Disease

With over 200,000 new cases per year, breast cancer accounts for nearly one-third of all new cancer diagnoses among women in the United States.⁷ Approximately 40,000 women will die of breast cancer in the U.S. alone.⁷ Worldwide, breast cancer is a major cause of cancer mortality, and was responsible for approximately 458,000 deaths in the year 2008.⁸

There is increasing recognition that breast cancer is comprised of several subtypes, each with distinct features.⁹ The majority of invasive breast cancers express the estrogen receptor (ER) and/or progesterone receptor (PR), and are HER2-negative. Patients with ER and/or PR-positive/HER2-negative (hereafter, designated as ER-positive) tumors tend to have a somewhat

better prognosis than patients with other tumor subtypes. However, in the metastatic setting, median survival is approximately 3 years and long-term remissions are relatively uncommon.

Initial treatment of ER-positive, metastatic breast cancer typically consists of endocrine therapy. Standard endocrine therapy options include tamoxifen, aromatase inhibitors, ovarian suppression, and fulvestrant. The choice of agent(s) varies depending on prior therapy, patient age and menopausal status, and anticipated tolerability. Although endocrine therapies can often be very effective, resistance almost invariably develops. While some patients may be salvaged with further lines of endocrine therapy, virtually all patients eventually progress through the available endocrine agents and require treatment with cytotoxic chemotherapy. For these reasons, in the metastatic setting, strategies to overcome or delay the emergence of endocrine resistance, particularly with treatments that are associated with a favorable toxicity profile in relation to standard cytotoxic agents, would be of great clinical value. Successful strategies could then be evaluated in the adjuvant setting. On average, among women with early-stage, ER-positive/HER2-negative tumors, the relative and absolute benefits of endocrine therapy far exceed that of chemotherapy.¹⁰ Thus, efforts to improve responsiveness to endocrine agents could ultimately have a substantial impact on overall breast cancer outcomes in patients with all stages of breast cancer.

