5. TREATMENT PLAN

Treatment must begin within 7 days of randomization. Treatment will be administered on an outpatient basis. Expected toxicities and potential risks as well as dose modifications for fulvestrant and ganetespib are described in Section 6 (Expected Toxicities and Dosing Delays/Dose Modification). No investigational or commercial agents or therapies other than those described below may be administered with the intent to treat the participant's malignancy.

Patients who enter the study and who are postmenopausal on the basis of GnRH agonist treatment must continue that treatment throughout the duration of the study.

A total of 71 patients will be enrolled in the study. Patients will be stratified according to whether or not they have measurable disease (by RECIST 1.1) at baseline and then randomized 1:2 to the two treatment arms:

Arm A: Fulvestrant (n=24)

Arm B: Fulvestrant plus Ganetespib (n=47)

Patients who are randomized to Arm A may cross over to Arm C (Fulvestrant plus ganetespib) at the time of centrally confirmed progression.

In both Arms A and B, each cycle will be ~28 days in length. Treatment will continue until disease progression (possibly the second progression on the combination therapy, if the patient was originally randomized to Arm A fulvestrant), unacceptable toxicity, withdrawal of consent, or death, whichever comes first. Follow up (specifically, tumor measurements as scheduled in

CONFIDENTIAL

This document is confidential. Do not disclose or use except as authorized.

the protocol) will continue until disease progression, withdrawal of consent, death, or the start of other anti-neoplastic therapy, whichever comes first.

Minor schedule changes owing to observed holidays, inclement weather, etc. are permitted. Patients may interrupt therapy for protocol-directed reasons (i.e. toxicity). From Cycle 3 forward, patients may also interrupt therapy for personal preferences (e.g., holidays, vacations). Treatment should resume according to protocol guidelines. Patients may not voluntarily omit fulvestrant at any time. From Cycle 3 forward, patients may not voluntarily omit more than 2 doses of ganetespib in a single cycle, except as detailed below. See Section 9.0 Study Calendar for additional details.

It is anticipated that some patients in Arm B or Arm C may either choose or be taken off of ganetespib for reasons other than disease progression (i.e., for toxicity or patient preference). The following guidelines apply:

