5.8 Duration of Survival and Adverse Event Follow Up

Participants will be followed for survival for up to 4 years after the last dose of protocol therapy or until death, whichever occurs first. Participants removed from study for unacceptable adverse events will be followed until resolution or stabilization of the adverse event.

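### Overall survival is analysed only at the PFS cut-off, with no comparative estimator named and no statement of how permitted crossover changes the contrast

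*Combined protocol and SAP*

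**What the plan says.** Section 1.3 lists as a secondary objective "To describe and compare overall survival (OS) between arms". In section 14.4 the OS paragraph includes all randomized patients, measures OS from randomization, says "OS will be estimated separately in Arm A and Arm B", and fixes the timing: "OS will be analyzed at the same time as the final analysis of PFS". It accepts that OS will be more heavily censored than PFS and that "this will limit the power to detect survival differences between the arms". It names no test, hazard ratio or confidence interval. The response and clinical benefit paragraphs of the same section each name a Fisher exact test.

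Section 14.2 places the final PFS analysis 20 months after a 20-month accrual, or 22 months after a 15-month accrual.

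Survival follow-up is described in two ways. Section 5.8 says "Participants will be followed for survival for up to 4 years after the last dose of protocol therapy or until death, whichever occurs first", and section 5.9 takes patients off study 4 years after the last study treatment dose. Section 5.1.16 collects survival every 3 months for at most 2 years from the last dose of the first assigned treatment. All four study calendars cite section 5.1.16 for survival status. It also refers to a final reporting of survival, without a date or a defined analysis.

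On crossover, section 5 says "Patients who are randomized to Arm A may cross over to Arm C (Fulvestrant plus ganetespib) at the time of centrally confirmed progression". Section 14.4 treats Arm C separately for toxicity and response but does not mention it for OS.

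**The concern.** There are two issues. First, survival may be collected for years after the single defined OS analysis, with no analysis specified for the later data. Second, with the assumed 4.0-month median PFS in Arm A and an exponential model, 1 − 2^(−12/4) = 87.5% of that arm will have progressed or died by 12 months. Study Calendar C calls for the first ganetespib dose within 2 weeks of documented progression. Crossover can therefore come early in the survival course. By randomized arm, the OS contrast is immediate ganetespib versus ganetespib that is optional and deferred to progression.

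The OS paragraph gives censoring as the only limitation. A small or absent OS difference could then be put down to few deaths, or taken as no effect of ganetespib on survival, when crossover may account for part of it.

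**Working it through.** **Reproducing the plan's timing figure.** Section 14.2 gives an effective sample of 20 + 40, medians of 4 and 8 months, accrual A = 20, follow-up F = 20, and a one-sided 0.05 log-rank test. With hazard λ = ln 2 / median, the expected event fraction is 1 − [exp(−λF) − exp(−λ(A+F))]/(λA).
- Arm A: 20 × 0.991 = 19.8 events. Arm B: 40 × 0.916 = 36.6. The total is 56.5, against 57 stated.
- Power at 57 events: Φ(√(57 × 1/3 × 2/3) × ln 2 − 1.645) = 79.4%, against 80% stated.

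The cut-off is therefore reproduced.

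**Deaths at that cut-off.** The plan states no OS median, OS events or OS power. Section 2.3 says "in the metastatic setting, median survival is approximately 3 years", which is disease background, so I treat median OS as an assumption. The same formula is applied to 71 patients with equal hazards in both arms:

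| Assumed median OS (months) | Deaths of 71 | Share |
|---|---|---|
| 24 | 40.7 | 57% |
| 30 | 35.2 | 50% |
| 36 | 30.9 | 44% |
| 42 | 27.5 | 39% |
| 48 | 24.8 | 35% |

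The 15 + 22 month scenario gives 30.6 deaths at a 36-month median. The share falls below half only if median OS exceeds about 29.6 months.

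**Deaths with later follow-up, 36-month median.**
- 4-year rule: 48 months plus 4 to 8 months on treatment gives 52 to 56 months per patient. 1 − 2^(−52/36) = 0.63 (44.9 deaths) and 1 − 2^(−56/36) = 0.66 (46.8).
- A simulation that ends each patient's follow-up 48 months after progression gives 47.2. A cut-off 44 months after accrual ends gives 45.7.
- 2-year cap: the same simulation with 24 months gives 29.0 deaths at the PFS cut-off and 33.2 in all, a gain of about 4.

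**Precision.** With 1:2 allocation, SE(log HR) = √(4.5/d), and the 95% interval runs from HR ÷ k to HR × k, where k = exp(1.96 × SE).
- d = 31: SE 0.381, k = 2.11.
- d = 46: SE 0.313, k = 1.85.
- 2-year cap: d = 29.0 gives SE 0.394 and k = 2.16; d = 33.2 gives SE 0.368 and k = 2.06.

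**Power.** For an assumed OS hazard ratio of 0.67 at one-sided 0.05, Φ(√(d × 2/9) × |ln 0.67| − 1.645) is 28% at d = 30.9 and 36% at d = 45.7. About 174 deaths would be needed for 80%.

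**Crossover.** The plan states no crossover share. A simulation assumed full ganetespib benefit from crossover onward, a 4-month median PFS in Arm A and a 36-month median OS:

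| True OS HR | 50% cross over | 80% | 100% |
|---|---|---|---|
| 0.67 | 0.78 | 0.85 | 0.91 |
| 0.50 | 0.64 | 0.74 | 0.82 |

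**The case against.** The plan is candid. Section 14.4 says that OS will be heavily censored and underpowered, section 14.2 calls the study exploratory, and no trial decision depends on OS. Reporting a secondary survival endpoint with the primary analysis is a disclosed choice, and a later analysis would still be far from powered. All of this stands, and it is why the point is a cheap improvement and not a flaw in the design.

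The 3-year median is general background. This trial enrols endocrine-resistant patients, with no limit on prior endocrine lines and up to one prior line of chemotherapy, so survival could be shorter. That stands too, and the death counts are given as a range for this reason.

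The gain depends on the longer follow-up. Under section 5.1.16, the section that the calendars cite, a later analysis adds little. This also stands, so reconciling the two periods comes first.

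Crossover is stated openly in the protocol, and OS is analysed by randomized arm. A reader might infer that the plan presents the OS contrast as ganetespib versus none. The documents nowhere say that; they leave the contrast undescribed. A reader might also infer that the later survival data are certain to go unused, but section 5.1.16 anticipates a final survival report and provides for death-index searches. What is missing is a date and a method.

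**Conclusion.** The point holds as a cheap improvement. The only defined OS analysis falls at the PFS cut-off, the OS paragraph names no comparative estimator although the objective is to compare, and it does not say how crossover changes the contrast.

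At a 36-month median, about 31 of 71 patients (44%) would have died at the cut-off, against about 45 to 47 under the 4-year rule. The confidence factor narrows from about 2.1 to 1.85. Under the 2-year cap the gain is about 4 deaths. These figures rest on exponential survival, uniform accrual, equal hazards in the two arms and treatment ending at progression.

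Two stronger readings are tempting. One is that OS would be judged on under half of the expected deaths. The documents give no expected number of deaths. The 44% is a share of patients under an assumed median, and the cut-off captures about 66% (30.9/47.2) of the deaths that 4-year follow-up would collect, or 87% (29.0/33.2) under the 2-year cap. The other is that crossover alone would make the arms look the same. In the simulation, even full crossover with full benefit leaves an attenuated difference (0.67 seen as 0.91), so crossover can shrink an effect toward null but does not by itself produce equality.

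**What to change.** 1. Reconcile the 2-year limit in section 5.1.16 with the 4-year limit in sections 5.8 and 5.9, including which last dose starts the clock. The date of a final OS analysis cannot be set until this is done.
2. In section 14.4, keep the OS estimate at the PFS cut-off and add a descriptive final OS analysis at the end of the reconciled follow-up: Kaplan-Meier curves and a hazard ratio with 95% confidence interval, by randomized arm. Link it to the survival reporting mentioned in section 5.1.16.
3. Report how many of the 24 Arm A patients crossed over, and when.
4. State that the contrast is immediate versus crossover-permitted deferred ganetespib, and that a null OS result will not be read as no effect of ganetespib on survival.

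The cost is one later rerun of the OS analysis and a few sentences. If the reconciled follow-up is the 4-year period already in sections 5.8 and 5.9, no follow-up is needed beyond what they provide. The downside is a final OS report that comes after the PFS report. If the reconciled period is short, the rerun adds little precision, but naming the estimator and stating the crossover contrast are still worthwhile.
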